10.1 Description

Azithromycin, or Zithromax, is supplied as an oral suspension in bottles containing azithromycin dehydrate powder equivalent to 1200 mg per bottle and the following inactive ingredients: sucrose, tribasic anhydrous sodium phosphate, hydroxypropyl cellulose, xanthan gum; FD&C Red #40, and flavoring including spray dried artificial cherry, crème de vanilla, and banana. After constitution, a 5 mL suspension contains 200 mg of azithromycin. This study will utilize the European Union formulation of the drug, which is comparable to the United States formulation.

10.2 Dosage

Azithromycin and placebo will be administered as a single oral 1.2 g dose. Individuals who are allergic to macrolides/azalides will not be enrolled in the study. We propose providing a 1.2 gm oral dose depending on immediate availability and formulation for azithromycin and placebo. A single 1 g dose of azithromycin in adults is approved for many common indications, including *Chlamydia trachomatis* urethritis and chancroid. This is also the dose used for treatment of trachoma, an ocular infection caused by *Chlamydia trachomatis*.

The efficacy of azithromycin for prevention of COVID-19 progression in SARS-CoV-2 positive patients is unknown, as is optimal dosing. Approved oral dosing for other indications includes:

- 500 mg as a single dose on Day 1, followed by 250 mg once daily on Days 2 through 5
- A single dose, give from 1 gm to 2 gm

Single dose regimens have clear advantages in adherence and regimen completion. The long half-life of azithromycin (68 hours for a single oral 500 mg dose) facilitates single dosing. However, this may come at the cost of increased risk of gastrointestinal symptoms.

The comparator group for this trial will be a masked placebo. We propose to use placebo due to the lack of safety and efficacy data for azithromycin in COVID-19 patients and because data generated by uncontrolled studies is unreliable.

10.3 Medication Procurement/Donation

Azithromycin and the placebo have been donated by the Pfizer Corporation. There will be no costs to acquiring the study medication. Pfizer, Inc. will ship azithromycin and placebo to the Proctor Foundation and study staff will send the treatment directly to patients. The lot numbers from the first shipment of drug are:

Placebo: P9640004

Azithromycin: 838900

10.4 Medication Quality Control

Medication will be stored at the Proctor Foundation between the temperature of 15°C to 30°C. The study coordinator and other staff will regularly check and record the study medication expiration dates. Expired medication will be discarded. The drug expires on November 30, 2021.

10.4.1 Drug Storage

The initial drug shipment from Pfizer, Inc. on May 22, 2020 will include 4,707 bottles of azithromycin (98 cartons) and 2,352 bottles of placebo (49 cartons). The drug will be stored at the UCSF Proctor Foundation at [name]. The drug will be kept between 59°F and 85°F in a locked room. Temperature will be monitored using a data logger. Data from the temperature data logger will be uploaded on a monthly basis.

The coordinator will maintain a smaller supply of drug stock at her place of residence until the shelter-in place order is lifted. The coordinator will keep at least 15 bottles of each treatment letter in stock at [name]. Temperature will be monitored at this location using a data logger. The temperature information will be uploaded monthly.

Logs will be maintained at both locations regarding stock and drug delivery on a weekly basis.

10.5 Packaging and Labeling

The study drug will be relabeled and packaged by UCSF laboratory personnel. Laboratory staff will completely remove the Zithromax labels and place the study label stickers on the bottle. The labels will indicate one of 6 letters: AAA, BBB, CCC, HHH, TTT, or VVV.

Labeling Example:

| | |
|---|--|
| ACTION Study Use before: 30 November 2021 For Oral Use Only Azithromycin 1200 mg (200 mg/5 ml) or Placebo Store at room temperature Caution: New Drug-- Limited by Federal law to investigational use Investigator Name: [name] UCSF FI Proctor Foundation [name] [contact] [contact] | Treatment Group TTT - Rx Only |
|---|--|

Once re-labeled, the drug will be given to the study coordinator. The study coordinator will place the corresponding treatment allocation into each participant's kit prior to sending it to the participant's address. The coordinator will use REDCap to determine each participant's treatment allocation letter.

10.6 Concurrent Medications

Participants are free to seek treatment for their COVID-19 symptoms outside of the study. Participants will be advised to avoid antacids containing aluminum or magnesium while in the study. Participants will be asked about concurrent medications taken at the follow-up questionnaires.

10.7 Measures of Treatment Compliance

Subjects will be asked to confirm if they took the study drug and on which date during the Day 3 questionnaire.

11 Adverse Event Monitoring and Safety Assessment

11.1 Adverse Events

Azithromycin has been extensively studied in humans for many indications, including community-acquired pneumonia and urethritis and cervicitis caused by *Chlamydia trachomatis* and *Neisseria gonorrhoeae*. Azithromycin is generally well-tolerated. The most common adverse events following azithromycin are diarrhea (5 to 14%), nausea (3 to 18%), abdominal pain (3 to 7%), and vomiting (2 to 7%). Rarer side effects include abnormal liver function, allergic

reactions, and prolongation of the QT interval. Diarrhea due to *Clostridium difficile* has been reported in rare cases.

Participants who are over 55 years of age and have taken hydroxychloroquine within the past 7 days will be excluded from this study due to concerns of QT prolongation.

Azithromycin is contraindicated in patients with known hypersensitivity to azithromycin, erythromycin, any macrolide or ketolide drug.

Azithromycin is also contraindicated in patients with a history of cholestatic jaundice/hepatic dysfunction associated with prior use of azithromycin.

The common adverse reactions that may occur will be explained in detail to the participants during the informed consent process. Participants will report any adverse events they have experienced during the Day 3 questionnaire. If a participant has a serious adverse event or any other concerns, they will be advised to contact their healthcare provider and/or 911. Participants can also email or call the study staff if they have any concerns.

Some adverse reactions were reported with azithromycin during the post-marketing period in adult and/or pediatric patients for which a causal relationship may not be established. These symptoms include:

Allergic: Arthralgia, edema, urticaria, and angioedema.

Cardiovascular: Arrhythmias including ventricular tachycardia and hypotension. There have been reports of QT prolongation and *torsades de pointes*.

Gastrointestinal: Anorexia, constipation, dyspepsia, flatulence, vomiting/diarrhea, pseudomembranous colitis, pancreatitis, oral candidiasis, pyloric stenosis, and reports of tongue discoloration.

General: Asthenia, paresthesia, fatigue, malaise, and anaphylaxis.

Genitourinary: Interstitial nephritis and acute renal failure and vaginitis.

Hematopoietic: Thrombocytopenia.

Liver/Biliary: Abnormal liver function, hepatitis, cholestatic jaundice, hepatic necrosis, and hepatic failure. [see *Warnings and Precautions (5.2)*]

Nervous System: Convulsions, dizziness/vertigo, headache, somnolence, hyperactivity, nervousness, agitation, and syncope.

Psychiatric: Aggressive reaction and anxiety.

Skin/Appendages: Pruritus serious skin reactions including erythema multiforme, AGEP, Stevens-Johnson Syndrome, toxic epidermal necrolysis, and DRESS.

Special Senses: Hearing disturbances including hearing loss, deafness and/or tinnitus, and reports of taste/smell perversion and/or loss

11.2 Adverse Event Monitoring

Adverse events will be formally monitored using an electronic questionnaire at Day 3. Participants will be asked to report any adverse events they have experienced since taking the

study drug. Participants will be asked if they have experienced the following adverse events since they last completed the study questionnaire:

- Nausea
- Vomiting
- Diarrhea
- Rash
- Abdominal pain
- Other

During the informed consent procedure, participants will be instructed that participation in the trial does not replace or represent their medical care. While there will be a study email address which participants can use to contact study investigators, it is not monitored full-time and is not a replacement for medical care, nor can the study staff offer medical advice. Participants will be instructed to contact their medical care provider for medical advice or call 911 in case of emergency.

Participants do not have to wait until the Day 3 questionnaire to report adverse events. Participants will be encouraged to contact the study staff at any time for any adverse events or concerns.

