5.2 Enrollment

Interested participants will be remotely screened for eligibility prior to enrollment. Participants can be screened by phone or by an electronic REDCap form accessible from the study website. If eligible, study staff will call the participant and collect informed consent electronically via DocuSign. Upon determining eligibility and signing electronic informed consent documents, study staff will ask the participant to provide their mailing address. Study staff will then mail the participant their randomized treatment allocation, self swabbing materials, and email an electronic baseline questionnaire. No contact between study staff and participants in this trial will take place as to minimize risk of infection spread. At the end of the screening questionnaire, we will collect phone number and email information from the eligible participants. We will also require patients to provide proof of their positive test result by uploading documentation through REDCap.

The data analyst will inform the coordinator daily of the new eligible participants. Coordinators will then call participants to review the study and informed consent form.

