5.5 Day 3 Assessment

Three days after treatment, participants will be asked to complete a brief adverse event survey. They will also be asked to self-collect sample specimens, if they are willing to. The first will be a nasal swab. The second will be a saliva swab. The third swab will be a rectal swab. The swab

kits will be mailed to the patient directly. Patients will have detailed instructions outlining how to collect the swabs. The swab procedure is outlined in Chapter 6. After collecting the swabs, the patient will mail the specimens back to the UCSF Proctor Foundation for analysis. Directions for shipping the samples back to the Proctor Foundation will be provided. We will mail participants pre-assembled category B biological substance shipping materials and a pre-paid shipping slip. Participants will call FedEx directly to schedule a pick-up or they will contact the study coordinator to schedule the pick-up for them.

Participants may opt out of the swab collection if they wish to do so. During the initial screening questionnaire, we will ask if participants are willing to collect the swabs. Participants can still participate in the trial, opting to only receive the medication and not perform the swabs.

Some participants may be willing to participate in the swab sub-study (determined at consent). These patients will be asked to collect saliva, rectal, and nasal swabs at Day 3. They will only collect these swabs once, and they will not collect Day 3 swabs as part of the main study.

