### 3.7. Timing of outcome assessments

Primary outcomes will be measured 14-days after enrollment. Additional visits will take place at 3, 7, and 21 days after enrollment. Protocol section 3.2 includes details about the trial profile.

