#### Secondary Outcomes:

- **Hospitalization and/or death by 14 days** after the electronic enrollment assessment.
- **Hospitalization/death by 21 days:** we will extend follow-up beyond the primary endpoint to capture any hospitalizations or death that progress more slowly and are not detected by 14 days.
- **Adverse events:** we will conduct an adverse event survey at Day 3 after treatment, including gastrointestinal side effects (nausea, vomiting, diarrhea, abdominal pain) and rash. We note that some COVID-19 patients report gastrointestinal symptoms, and this survey will provide data on whether azithromycin causes additional gastrointestinal effects beyond those symptoms.
- **Prevalence of positive swabs:** we will compare the prevalence of SARS-CoV-2 positive swabs at Day 3 after treatment in self-collected nasal, saliva, and rectal swabs in azithromycin compared to placebo-treated participants.
- **Viral load:** we will assess viral load by RT-PCR in self-collected nasal, saliva, and rectal swabs at Day 3 after treatment.
- **Mortality:** we will collect emergency contact/next of kin information during the baseline questionnaire. We will follow-up with the emergency contact if participants are lost to follow-up at the Day 14 and Day 21 questionnaires to assess mortality and hospitalization outcomes.
- **Genetic macrolide resistance determinants:** We will evaluate the prevalence of genetic macrolide resistance determinants *ermB*, *mefA/E*, and *mphA* by targeted PCR in rectal samples collected at Day 3 after treatment.
- **COVID-19 symptoms at 21 days:** we will ask patients about COVID-19 symptomology during each online questionnaire, including cough, fever, myalgia, anosmia, shortness of breath (and related abilities such as ability to walk across a room or up a flight of stairs), fatigue, conjunctivitis, and orthostatic symptoms.
- **Number of emergency room visits:** during each online questionnaire we will survey patients about any emergency room visits (with stays <24 hours) that occurred since their last survey.
- **Number of household members with COVID-19 (confirmed or symptomatic):** during each online questionnaire we will ask participants how many of their household members have symptoms of COVID-19 or confirmed disease.

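### Protocol 11.2 gives two recall windows for the Day 3 adverse-event survey; the checklist's window opens before dosing and would dilute the comparison between arms

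*Protocol*

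**What the plan says.** Protocol 11.2 schedules one structured survey: "Adverse events will be formally monitored using an electronic questionnaire at Day 3". It then states the recall period twice. The general request reads "Participants will be asked to report any adverse events they have experienced since taking the" study drug. The next sentence, which introduces the six-item checklist, reads "Participants will be asked if they have experienced the following adverse events since they last completed the study questionnaire".

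The timeline in Protocol 3.8 puts the baseline questionnaire at Day 0, treatment at Day 1 and the adverse-event questionnaire at Day 3. Protocol 5.2 describes how the baseline form and the drug go out: "Study staff will then mail the participant their randomized treatment allocation, self swabbing materials, and email an electronic baseline questionnaire". Protocol 10.7 has the Day 3 form also ask whether the drug was taken and on what date.

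Adverse events are a secondary outcome (Protocol 3.4.2, SAP 6.1). Both documents accept that COVID-19 itself can cause gut symptoms, and the SAP states the purpose: "this survey will provide data on whether azithromycin causes additional gastrointestinal effects beyond those symptoms". SAP 6.2 compares the arms by a difference in proportions, with a 95% confidence interval and a permutation test. It notes that events accumulate through Day 3 but does not say when counting begins.

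**The concern.** The two sentences in 11.2 define different outcomes, and the longer window is the one attached to the named items that feed the secondary analysis. A participant with COVID-19 nausea or diarrhea after completing the baseline form, but before taking the drug, has no event under the first sentence and an event under the second. Nothing in the SAP decides between them.

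The survey is meant to isolate what azithromycin adds to the illness. Events that precede the dose cannot be caused by it, so counting them in both arms raises the background and reduces the ability to see a real excess. The question has weight in this trial because Protocol 10.2 itself mentions a possible increase in gastrointestinal symptoms as the price of single dosing.

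**Working it through.** The plan gives no expected rate, power or sample size for the adverse-event comparison, so there is no stated figure to reproduce. The target of 455 was set for the primary outcome.

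**1. Where the checklist window starts.** In Protocol 3.8 the last questionnaire before Day 3 is the baseline form at Day 0, and the dose is at Day 1. The pre-dose stretch is nominally one day, and longer if delivery or dosing is late. The documents do not say how often that happens.

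**2. Effect on the contrast.** Let p be the risk of an event after the dose and q the probability of a pre-dose symptom, equal in both arms and independent of later events.

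- Reported risk = 1 − (1−q)(1−p)
- Reported difference = (1−q)(p₁ − p₀)

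If p₁ = p₀ the difference is zero for every q, so the wording creates no false signal.

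**3. Numbers.** Assume post-dose risks of 5% on placebo and 15% on azithromycin. Neither is stated in the documents. For scale, Protocol 11.1 gives 5 to 14% for diarrhea and 3 to 18% for nausea on azithromycin, and no placebo rate. The values of q are also assumed.

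| q | Placebo | Azithromycin | Difference |
|---|---|---|---|
| 0 (window from dose) | 5.0% | 15.0% | 10.0 points |
| 10% | 14.5% | 23.5% | 9.0 points |
| 20% | 24.0% | 32.0% | 8.0 points |
| 30% | 33.5% | 40.5% | 7.0 points |

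For q = 20%, for example: 1 − 0.80 × 0.95 = 24.0% and 1 − 0.80 × 0.85 = 32.0%.

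**4. Why this is an upper bound on the loss.** A symptom that begins before the dose and persists after it is reported under either window. Let r be the share of pre-dose symptoms that persist. The window from the dose then gives a difference of (1−qr)(p₁−p₀), so the ratio of the two differences is (1−q)/(1−qr). At r = 0 this is (1−q), as in the table. At r = 1 it is 1, and the choice of window makes no difference.

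**5. Effect on power, as an illustration.** Assume 5% on placebo and a drug that adds 10 points of risk among those otherwise event-free: 1 − 0.95 × 0.90 = 14.5%. Power is by the normal approximation, two-sided 0.05, 2:1 allocation, at N = 455 and at 0.8 × 455 = 364 (the SAP's 20% loss to follow-up).

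| q | Difference | Power, N = 455 | Power, N = 364 |
|---|---|---|---|
| 0 | 9.5 points | 89% | 81% |
| 5% | 9.0 points | 72% | 62% |
| 10% | 8.6 points | 58% | 48% |
| 20% | 7.6 points | 39% | 32% |
| 30% | 6.7 points | 28% | 23% |

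Power falls faster than the difference because the added background also raises the variance. These figures too take r = 0, so they show the worst case for each q.

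**The case against.** The strongest reply is that the general sentence in 11.2 already limits reports to the time after the dose, and that this is protocol prose rather than the form. The Day 3 questionnaire is not among the documents, so the wording participants actually saw cannot be checked. That stands, and it makes this a contradiction to resolve, not a pre-dose window the sponsor has chosen. It is also fair that the nominal gap is one day, that q has no source, and that COVID-19 gut symptoms arising after the dose remain under either window. A corrected window removes only part of the background.

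Four stronger readings are tempting but not supported:

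- **That nothing is surveyed after Day 3, or that later reactions surface only if volunteered.** Symptoms and hospitalization are asked at Days 7, 14 and 21 (Protocol 3.8). Emergency room visits are asked about and followed up (3.4.2, 5.12), vital status is collected (14.1), and serious adverse events are recorded to Day 21 (SAP 6.5). What is true is narrower: the gut and rash checklist is not scheduled again, and those items are not among the follow-up symptoms listed in 3.4.2.
- **That Day 3 comes too early because of the drug's half-life.** The protocol says "The long half-life of azithromycin (68 hours for a single oral 500 mg dose) facilitates single dosing", but nothing in the documents links elimination to the time when gut reactions or rash begin.
- **That Day 3 may be counted from enrollment.** SAP 3.7 does say "Additional visits will take place at 3, 7, and 21 days after enrollment", but that is a general schedule. The text specific to adverse events counts from treatment, as in Protocol 5.5: "Three days after treatment, participants will be asked to complete a brief adverse event survey". Protocol 3.4.2 and SAP 6.1 and 6.2 agree.
- **That risk ratios show the damage.** They shrink faster than the difference, but the planned adverse-event contrast is the difference.

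**Conclusion.** The point holds as an internal contradiction in Protocol 11.2 that the SAP leaves open. If the checklist wording governs, the planned risk difference is pulled towards zero by at most the factor (1−q). An assumed 10-point difference becomes 9 points at q = 10% and 8 points at q = 20% in the worst case, and less is lost to the extent that pre-dose symptoms persist past the dose. The size rests on an unknown q, on equal q in the two arms, and on independence of pre-dose and post-dose events. The consequence is lost sensitivity for a secondary safety outcome. It does not bias the result towards harm and does not touch the primary outcome. The point is minor, but worth correcting because the remedy is nearly free.

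**What to change.** Use a single window for the checklist in Protocol 11.2, starting at the dose, and make the form match. Anchor it to the dose date that Protocol 10.7 already collects on the same Day 3 form. State that start in SAP 6.2 beside the note on cumulative counting. Report participants who had not dosed when they completed the survey as a separate row by arm. The cost is a change of questionnaire wording and one line in the SAP. If forms already in use carried the longer window, say so when reporting, and note that the difference may be diluted.

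Optionally, repeat the same six items on the existing Day 7 questionnaire, since the checklist is otherwise given only once. This needs no new contact and makes that form slightly longer.

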11.3 Serious Adverse Events

A Medical Monitor for the trial will be designated by the study lead investigators. The Medical Monitor will review all SAE's that occur and evaluate the likelihood of an association to the study drug. If deemed possibly related to the study drug by the Medical Monitor, the SAE will be forwarded to the DSMC and IRB if necessary. The Medical Monitor for this study will be [name], an internal medicine and infectious disease specialist at UCSF. The Medical Monitor will review serious adverse event cases ideally within 24 to 48 hours. Other adverse events will be analyzed by arm at the end of the study or per request from the DSMC.

Any serious adverse events will be reported to Pfizer. An ISR SAE Form (Investigator-Sponsored Research Serious Adverse Events Form) will be completed by study personnel for each event and sent to [contact].

An SAE is defined as any adverse event that:

- Results in death
- Is life-threatening (i.e., causes an immediate risk of death)
- Results in persistent or significant disability or incapacity
- Results in a congenital anomaly or birth defect
- Changes the risk/benefit ratio of the study
- Any cardiovascular related or unrelated serious adverse event

Or that is considered to be:

- An important medical event

Serious adverse events will be reported to Pfizer, the Data and Safety Monitoring Board and the Institutional Review Board at the University of California, San Francisco. Any event deemed to be definitely, probably, or possibly related and is serious or unexpected will be reported to the IRB within 5 days. Deaths and life-threatening events will be reported immediately.

UCSF will be responsible for discerning which medical occurrences meet the serious adverse event criteria. UCSF personnel will then fill out an ISR SAE form and submit to Pfizer no later than 48 hours from UCSF's awareness date. UCSF awareness date should be noted on the ISR form. UCSF will report SAEs around the clock, 7 days a week. UCSF should not report duplicate reportings of SAEs and provide the causality determined by the Medical Monitor.

Serious adverse events will also be reported to the Food and Drug Administration (FDA). UCSF will be in compliance with the FDCA (21 USC 301 et seq) and Title 21 of the code of federal regulations. UCSF will report any unexpected fatal or life-threatening suspected adverse reactions to the FDA no later than 7 days after initial receipt. UCSF will also report SAEs, findings suggesting significant human risk, and/or clinically important events that increase the rate of SAEs within 15 days after determining the information qualifies for reporting. UCSF must always cite the IND number 149526 on all correspondence. Additionally, UCSF will submit an annual progress report within 60 days of the anniversary of the IND active date (4/18/2020).

12 Protection of Human Subjects

The research team will obtain formal ethical approval prior to the study start. Informed written consent will be collected from all participants electronically due to the remote nature of the study. A research team member will describe the study to participants in depth including information about the treatment and study activities. If, at any time, a participant wishes to withdraw from the study, they will be free to do so.

A Data and Safety Monitoring Board (DSMB) will be empaneled to review patient data throughout the course of the study. The Board will meet to review and approve study procedures prior to trial commencement and will review reports of serious adverse events and interim safety and efficacy analyses. Members of the DSMB will have expertise in infectious disease, epidemiology, biostatistics, and randomized controlled trials.

